### **Appendix IV- Study Variable Summary**

#### Phone Call Study Patient Variates

BASELINE PATIENT DATA
First name
Last name
Zipcode
Medical record number
Established Primary Care Yes
No

Health Literacy BHLS Education level

Race Black White

Latino Non-white Hispanic

Multiple Races Unknown

Primary Language English

Spanish Arabic Other

Number of Hospitalizations in Prior Year

Complicating Baseline Comorbidities (Natural Language Processing)

Congestive heart failure

COPD

Readmission penalty dx - AMI, HF, PNA, COPD,

CABG, Total hip/knee repair, and stroke

Diabetes

Outpatient hospice Substance abuse Depression INDEX HOSPITALIZATION DATA

Intervention Arm Encounter Number Date of admission Time of admission

Admission day of the week Admission Diagnosis #1 Admission Diagnosis #2 Admission Diagnosis #X Highest bed level

Floor ICU Discharge Service Riven Morgan

> Geriatrics Palliative Care

Discharge Diagnosis #1 (ICD-10)
Discharge Diagnosis #2 (ICD-10)
Discharge Diagnosis #3 (ICD-10)
Discharge Diagnosis #4 (ICD-10)
Discharge Diagnosis #X (ICD-10)

Discharge Date Discharge Time

Discharge Location/Disposition

Readmission penalty dx cohort- AMI, HF, PNA, COPD, CABG, Total hip/knee repair, and stroke

Number of medications upon discharge

VUMC Cornelius Readmission Risk Score Patient satisfaction (Press Ganey Score, 1-5)

READMISSION HOSPITALIZATION DATA

Date of admission Time of admission Admission Diagnosis #1 Admission Diagnosis #2

Admission Diagnosis #X Highest bed level Floor

ICU
Discharge Diagnosis #1 (ICD-10)
Discharge Diagnosis #2 (ICD-10)
Discharge Diagnosis #3 (ICD-10)

Discharge Diagnosis #4 (ICD-10)

Discharge Diagnosis #X (ICD-10)

Readmission penalty dx - AMI, HF, PNA, COPD, CABG, Total hip/knee repair, and stroke

Discharge Date
Discharge Time
Discharge Location

Patient satisfaction (Press Ganey Score, 1-5)

Extra-Institutional Data

Survival Data (at 30 days)

Non-VUMC TN Readmission (at 30 days post VUMC

admit)

(minimum data = yes/no)

CALL INTERVENTION DATA

1st Contact

Time of first call Date of first call

Final Contact

Time of Final Contact Date of Final Contact

Call attempts

1 2 3

Not eligible AMA Facility Placement Deceased

Already seen in clinic CRC patient

Patient currently admitted/readmitted

Call status

Success

Unsuccessful - Wrong Number

Unsuccessful - Refused

Unsuccessful - Patient Call Back Requested

Unsuccessful - Patient Not Available

Unsuccessful - No Answer

Unsuccessful - Patient Never Admitted

Unsuccessful - Left a Message

Unsuccessful - Patient in Hospital

Unnecessary (already seen in clinic)

Can teach back self care

Yes No

Partial

Pt aware of follow up appointment

Yes

Able to teach-back follow up appointment

Yes No Partial

New Meds Upon Discharge Yes

No

Able to teach-back current medications dosing

Yes

No

Partial

Has obtained medications prescribed at discharge

Yes

No

Discharge Implementation Assistance Required

Provider contacted for pain/symptom/complication

Durable Medical Equipment Facilitated Home Health Connection

Referral to PCP (pt instructed to call) Referral to ED (pt instructed to go)

Case Management/Social Work Assistance Requested

Medication Dose Change by Call RN Pharmacist assistance requested Provider assistance requested Planned Follow Up Appt Reminder Planned Follow Up Appt Scheduled

Medication education provided

Total Intervention Time (call prep, phone time, care coordination)

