### Secondary Analyses:

- Subgroup Analysis of Primary Outcomes (forest plots + interaction analysis)
- Survival/Frequency Plot of Readmission events (0-45 days)
- Descriptive Demographics of Controls, Reached, Not Reached
- Heat Map of readmission rates by zip code

Figure 1 - Study Design Schematic and Enrollment Projection

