#### STUDY TIMELINE: UPDATED

- 1. Adult Executive Quality Committee 3 month Update June 21, 2017
- a. Analysis: [name] (descriptive, no outcome data)
  - Table 1 Patient demographics
  - Overall VUMC readmission rate
  - Summary of phone call nurse patient interventions
- b. Presenters: [name], [name], [name]
- 2. Blinded Interim Analysis 50% patient enrollment ~July 2017
- a. Content ([name])
  - 2 week analysis window: Alpha 0.005, no stopping/futility rules
  - Patient demographics (by study arm, Table 1)
  - VUMC readmission rate by study arm and assessment of significant difference
  - Pre-specified subgroup analysis for readmission yes/no
  - Will not include the reachability index at this time.
  - Will only use death data from VUMC and available Patient Satisfaction data
  - See Appendix V for details
- b. Safety Review August 2017
  - Safety Committee Members: [name], [name], [name]
  - Review of Discharge Phone Call RN's daily reports to her supervisors for safety issues.
  - Interim Analysis Preparation and Presentation: [name]
- 3. Enrollment End 100% patient enrollment end: ~Sept 20, 2017
- a. Readmit f/u end: ~Nov 5, 2017
- b. Freeze database after Patient Satisfaction data (2mo lag) included: ~Nov 20, 2017
- c. Re-open database to add death + external hospital readmission data (6-8mo lag): ~May 20, 2018
- d. Death date source: VUMC EHR
- e. External hospital readmission data source: Vanderbilt Health Affiliated Network (VHAN)
- 4. Adult Executive Quality Committee Presentation Study End Early Findings Jan 2018
- a. Final analysis findings, except for death data
- b. 2 week analysis window: Alpha 0.048
- 5. Final Analysis June 2018
  - a. Content ([name] and [name])
    - 2 week analysis window: Alpha 0.048
    - Patient demographics (by study arm, Table 1)
    - VUMC readmission rate by study arm and assessment of significant difference
    - Pre-specified subgroup analysis for readmission yes/no
    - Identical to the Interim Analysis plan except all patient satisfaction, external hospital readmission, and mortality data will be included.

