#### Outcome Measures

### Primary Outcome for this study is readmission within 30 days

Secondary Outcomes include evaluating: The primary outcome of readmission within 30 days within prespecified subgroups (age, gender, race, health literacy level, established primary care status, patient satisfaction, Medicare readmission penalty diagnosis status, readmission risk score), patient satisfaction between the study arms measured as mean Hospital Consumer Assessment of Healthcare Providers and Systems (HCAHPS) patient satisfaction scores, all cause VUMC ED visits, the need for assistance with discharge plan implementation, and mortality within 30 days.

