### Study Length and Timeline

The informatics run-in period will begin February 7th, 2017 to test the Study Data Flow and integrity of the randomization process. Official study enrollment will begin February 20th, 2017. Patients will be randomized the morning after hospital discharge. Those receiving a call will be contacted within 7 days of hospital discharge. We will obtain interim impact estimates of the discharge phone call intervention at 50% enrollment for 80% power (See the *Study Timeline*, on page 2), and conduct the definitive analysis at 100% enrollment. In addition, the analyses will account for a 30 day re-admission observation window. Fifteen additional days will be added to the follow-up period to assure re-admissions are not minimally deferred to just after the 30 days period. Run-in period patient cases will be used to test the study data extraction and database upload process prior to the planned study analyses. This will permit us to troubleshoot unforeseen data collection challenges. Given the sample size considerations noted above, we estimate a study length of 7 months with enrollment completion in September of 2017, primary outcome follow-up ending in November of 2017, and data collection completed in (due to data lags for patient satisfaction, external hospital readmission, and mortality data) May of 2018.

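### Appendix IV starts the 30-day external readmission window at VUMC admission and requires only a yes/no, while the rest of the design implies a clock that starts at discharge

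*Combined protocol and SAP*

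**What the plan says.** Appendix IV (Study Variable Summary, Extra-Institutional Data) contains the only definition of a window for readmission outside VUMC: "Non-VUMC TN Readmission (at 30 days post VUMC", completed on the next line by the word *admit*. Beneath it is the data requirement: "minimum data = yes/no". For readmissions at VUMC the same appendix lists date and time of admission. It also lists admission and discharge dates and times for the index stay.

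Outcome Measures gives the primary endpoint without a start point: "Primary Outcome for this study is readmission within 30 days". Study Length and Timeline places randomisation after the index stay ("Patients will be randomized the morning after hospital discharge"), says that "the analyses will account for a 30 day re-admission observation window", and extends follow-up: "Fifteen additional days will be added to the follow-up period to assure re-admissions are not minimally deferred to just after the 30 days period". Study Arms allows call attempts until post-discharge day 7.

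The Study Timeline gives "Enrollment End 100% patient enrollment end: ~Sept 20, 2017" and puts the end of readmission follow-up at about November 5. It re-opens the database about May 20, 2018 to add external readmissions, and includes them in the final analysis. The Data Collection section treats missing external readmissions as an important weakness of such studies. It plans to draw records of hospital admissions and discharges from the affiliated network (VHAN).

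**The concern.** Two parts of the plan measure 30 days from different starting points. If a programmer or data provider follows the Appendix IV line as written, the time spent in the index stay uses up part of the external window. A VUMC readmission on post-discharge day 25 would count for every patient. An external readmission on the same day would count only if the index stay lasted no more than 5 days.

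A combined rate would then not be a 30-day post-discharge rate. The shortfall would also depend on length of stay, so external capture would be poorest in long-stay patients. The yes/no minimum matters because a bare flag carries no date from which the window could be rebuilt. External data are being added to close a gap in capture, and this line would leave part of that gap open.

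**Working it through.** **1. Which clock the design implies.** No section states in words that the 30 days run from discharge, so this is an inference. It rests on three items:
- Randomisation takes place the morning after discharge.
- The call window is counted from discharge (day 7; the Appendix III form makes patients ineligible after 168 hours, and 168/24 = 7 days).
- From September 20 to November 5, 2017 is 10 + 31 + 5 = 46 days. This fits 45 days of follow-up for the last patient, counted from discharge or randomisation.

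**2. External window under the literal entry.** With L = length of index stay in days:

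post-discharge days covered = 30 − L, and not below 0.

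Under a flat readmission hazard over 30 days (an assumption), the share of external 30-day events missed is L/30.

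The documents give no mean, median or distribution of L; Appendix V only lists it as a covariate. The one stay shown is the specimen record in Appendix III, from March 10 at 16:30 to March 12 at 11:55. That is 43.4 hours, or 1.81 days. The other rows are assumed values.

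| L (days) | Post-discharge days covered | Share missed, flat hazard |
|---|---|---|
| 1.81 (specimen form) | 28.2 | 6% |
| 3 | 27 | 10% |
| 5 | 25 | 17% |
| 7 | 23 | 23% |
| 10 | 20 | 33% |
| 14 | 16 | 47% |
| 30 or more | 0 | 100% |

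At L = 23 the external window closes on post-discharge day 7, the last day on which a call may be attempted. If readmissions cluster soon after discharge, the shares missed are smaller than L/30.

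**3. Scale against the planned power.** The Study Summary gives 1778 per arm for 13.5% versus 10%, 90% power, chi-square. With the pooled-variance formula and no continuity correction,

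n = [z(1−α/2)·√(2p̄q̄) + z(1−β)·√(p₁q₁ + p₂q₂)]² / (p₁ − p₂)²,

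where p̄ = 0.1175. At two-sided α = 0.05: (1.960 × 0.4554 + 1.2816 × 0.4547)² / 0.035² = 1777. The plan's figure is reproduced. At the final-analysis α of 0.048, power with 1778 per arm is 89.7%.

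For illustration, let external events be a share s of all readmissions, with the same L for everyone and a flat hazard. Both rates are then multiplied by k = 1 − s·L/30:
- s = 10%, L = 3: k = 0.99; rates 13.4% and 9.9%; power 89.4%.
- s = 20%, L = 5: k = 0.967; rates 13.1% and 9.7%; power 88.6%.
- s = 30%, L = 10: k = 0.90; rates 12.2% and 9.0%; power about 86%.

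Neither s nor L is in the documents. Table 1 labels the control rate as a historical VUMC rate. If that excludes external events, they would come on top of 13.5%, and the loss would trim the addition and leave the planning rate intact. These figures show scale only.

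**4. Direction.** L is fixed before randomisation, so its distribution should be the same in both arms in expectation, and so should the truncation.

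**5. Whether the window can be rebuilt.** Index discharge dates are held. Rebuilding therefore needs only the external admission date, from an extract that reaches at least 30 days past discharge. The yes/no minimum guarantees neither. The extraction described under Data Collection would supply the date.

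**The case against.** The strongest reply is that this is one word in a shorthand variable list, plausibly a slip for discharge, and that the operational text points the other way. That is fair, but nothing in the documents settles it. The variable list is what a data request would be written from, and the remedy is the same whether or not it is a slip.

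A reader might infer that the error is permanent. The documents do not support that. Yes/no is a floor, the Data Collection section plans a fuller extract, index dates are kept, and external data arrive only about May 2018.

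A reader might also infer that external events are shut out of the "Survival/Frequency Plot of Readmission events (0-45 days" and the Cox model. That would follow only if nothing beyond the flag were obtained. The plan does not commit external events to those analyses in any case: Appendix V labels its time-to-event item as VUMC readmission, and Statistical Analysis presents the Cox model as exploratory and not powered.

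Finally, the cost may be small. The only stay shown is under two days, the larger percentages rest on assumed stays, and they apply to external events alone. All of this stands and limits the size of the point. It does not remove the conflict between the two anchors.

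**Conclusion.** The point holds as an inconsistency to be reconciled before the external data are requested. Followed literally, Appendix IV shortens each patient's external window by the length of stay, so a combined rate would mix two windows and undercount external events, most in long-stay patients. That the VUMC window starts at discharge is a sound inference, though no section states it.

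The size is unknown. The 10% to 47% range depends on assumed stays of 3 to 14 days and a flat hazard. The illustrated power loss, from 89.7% to between 89.4% and about 86%, depends also on an assumed external share of 10% to 30%. A reader might infer a bias between arms; the documents give no ground for one, because length of stay precedes randomisation. The harm is a poorly defined endpoint and some lost events. It becomes irrecoverable only if the flag alone is obtained or the extract is cut at 30 days after admission.

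**What to change.** - State one anchor, index discharge, for both VUMC and external readmission, in Outcome Measures and in Appendix IV.
- Replace the Appendix IV entry with the admission date of any external inpatient readmission from day 0 to day 45 after index discharge. Make that date the required item in the VHAN request, in line with the extraction described under Data Collection.
- Derive the 30-day yes/no from that date and the index discharge date.
- If a hospital can supply only yes/no, report its events separately and do not pool them into the 30-day rate.
- Using the external dates in the 0 to 45 day plot and the Cox model is optional.

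The cost is a line in the variable list, a matching line in the data request, and a short clarification of the endpoint. External data are not due until about May 20, 2018, so the plan's own timetable leaves room for it.

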### Appendix V – Interim Analysis Plan INTERIM ANALYSIS PLAN

- 1. Consort Diagram (Consort Diagram Figure 1)
  - a. Pts Enrolled
  - b. Pts Randomized
  - c. Post-Randomization exclusions by arm total count and rate (including reasons with counts)

#### 2. Adverse Events Summary

- a. All Pts: Results of a debriefing with the Medicine Patient Care Center for incidents that
  - Raised concerns that the phone calls may introduce harm or create and issue
     (i.e. MVC s/p picking up call from the Phone call RN, d/c plan confusion introduced by phone
     call RN involvement, etc)
- b. Intervention Pts: Unmet need upon initial discharge (Summarized in *Table 3*, see below)

### 3. Co-Variate Distribution (*Table 1*)

- a. Patient: Age, sex, zip code, established primary care, BHLS, education level, race, primary language, VUMC admits in prior 6 mo, VUMC ED visits in prior 6 mo, PMHx (7 readmit penalty diagnoses, DM, outpatient hospice, substance abuse, depression)
- b. Index Admission: Admit diagnosis, # meds upon discharge, Cornelius score, Any ICU time, meds-to-beds program exposure, %weekend discharges, % discharges after 4pm, Hospital LOS
- 4. Outcome Analysis (ITT analysis for stat significant differences)
  - a. VUMC Readmission Rate
    - i. Rates (*Table 2* 2x2 Table)
    - ii. Descriptives for proportion readmit penalty diagnosis
  - b. Time to VUMC readmission
    - i. Kaplan-Meier Curve (Figure 2)
  - c. VUMC ED Revisit Rate
  - d. Patient Satisfaction (Press Ganey)

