#### Inclusion Criteria

The study will include VUMC patients discharged after an inpatient status hospital stay on the following General Medicine services: Riven, Morgan, Geriatrics, and Palliative Care.

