#### Statistical Analysis

In our univariate analysis, differences among these patient characteristic groups will be assessed using the continuity corrected chi-square test or Mann-Whitney test for continuous outcomes and the Kruskal-Wallis test for categorical outcomes. In our multivariate analysis, we will examine the relationship between treatment assignment and our secondary endpoints using logistic regression. The study is not powered for a time-to-event analysis; however, we will explore time-to-readmission using the Cox proportional hazard model to understand the timing of when readmissions occur. In order to provide VUMC Leadership with preliminary efficacy data, we will perform an interim analysis at 50% enrollment ( $\sim$ 3.5 months) followed by the final analysis at study completion months ( $\sim$ 7 months). See **Appendix V** for details. We have pre-specified an  $\alpha$ -level of significance of 0.05 with penalties for a mid-study interim analysis per the O'Brian-Fleming alpha spending function allowing for an  $\alpha$ -significance level of 0.005 for the interim analysis and 0.048 for the final analysis.

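### The readmission curve is a Kaplan-Meier plot with no rule for death before readmission, in a cohort that enrols Palliative Care patients; cumulative incidence curves would be better

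*Combined protocol and SAP*

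**What the plan says.** The primary endpoint is binary: "Primary Outcome for this study is readmission within 30 days" (Outcome Measures). The Study Timeline treats it as yes or no, and Appendix V, item 4, puts the "VUMC Readmission Rate" in a 2x2 table by intention to treat.

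Time to readmission appears in three places:
- Appendix V, item 4: "Kaplan-Meier Curve (Figure 2".
- Statistical Analysis: "we will explore time-to-readmission using the Cox proportional hazard model", after the statement "The study is not powered for a time-to-event analysis".
- Study Summary, Secondary Analyses: "Survival/Frequency Plot of Readmission events (0-45 days".

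Appendix V is the interim plan. The Study Timeline makes the final analysis the same apart from the later satisfaction, external readmission and mortality data, so the Kaplan-Meier plot carries over.

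The enrolled services are "Riven, Morgan, Geriatrics, and Palliative Care" (Inclusion Criteria). The Exclusion Criteria remove in-hospital deaths and discharges to inpatient hospice. Outpatient hospice is a baseline covariate (Appendices IV and V), so such patients can be enrolled. Thirty-day mortality is a separate secondary outcome. The Study Timeline names the VUMC electronic record as the source of death dates, and Appendix IV lists survival at 30 days.

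The documents mention no censoring rule, competing risk, cumulative incidence function, or combined readmission-or-death endpoint.

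**The concern.** A patient who has died cannot be readmitted. If that patient is censored at death, Kaplan-Meier estimates readmission as though the patient could still return at the same rate as the survivors. One minus Kaplan-Meier then exceeds the proportion actually readmitted. Post-discharge deaths are foreseeable in this cohort, and the plot runs to day 45, so the gap has time to grow.

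Two things are at stake. A reader comparing the curve at day 30 with the 2x2 table would find two different readmission rates for the same arm. And because a death without readmission falls in the not-readmitted cell, a readmission difference is harder to interpret if the call also changes deaths.

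**Working it through.** **The plan's own figure.** The Study Summary gives 1778 per arm for 13.5% against 10%, 90% power, chi-square. With z = 1.960 and 1.2816 and a mean proportion of 0.1175:

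n = [1.960 × √(2 × 0.1175 × 0.8825) + 1.2816 × √(0.135 × 0.865 + 0.10 × 0.90)]² / 0.035² = (0.8926 + 0.5828)² / 0.001225 ≈ 1777.

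This reproduces the stated figure at alpha 0.05; at alpha 0.048 it is 1796. Neither calculation involves deaths or the curve.

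**Model for the curve.** Inputs from the documents are a control readmission rate of 13.52% at day 30 (Power Calculation), 10% in the intervention arm (Study Summary), and a 45-day horizon. The proportion dying unreadmitted by day 45 is an assumption: 1%, 4% or 10%, equal in the two arms. Hazards r (readmission) and d (death) are taken as constant.

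- True cumulative incidence of readmission at t: r/(r+d) × [1 − exp(−(r+d)t)], set to the stated rate at t = 30.
- Deaths without readmission by day 45: d/(r+d) × [1 − exp(−45(r+d))], set to the assumed value.
- One minus Kaplan-Meier with deaths censored: 1 − exp(−rt).

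Example, control arm, 10% deaths: r = 0.005045 and d = 0.002628 per day. Cumulative incidence at day 30 is 0.6575 × (1 − e^−0.2302) = 13.52%. One minus Kaplan-Meier is 1 − e^−0.15135 = 14.05%.

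| Assumed deaths by day 45 | Control 1−KM, day 30 (true 13.52%) | Excess, day 30 | Control 1−KM vs true, day 45 | Excess, day 45 | Arm difference in 1−KM, day 30 (true 3.52) |
|---|---|---|---|---|---|
| 1% | 13.57% | 0.05 | 19.65% vs 19.54% | 0.11 | 3.53 |
| 4% | 13.72% | 0.20 | 19.86% vs 19.43% | 0.43 | 3.58 |
| 10% | 14.05% | 0.53 | 20.31% vs 19.20% | 1.11 | 3.67 |

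The arm difference therefore shifts by 0.01 to 0.15 points. Under the heavier assumption that 1% to 10% die unreadmitted by day 30, the control excess at day 30 (from 13.5%) is 0.07 to 0.76 points, and the difference moves from 3.50 to between 3.52 and 3.70.

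**If deaths differ by arm.** Hold the readmission hazard equal at r = −ln(0.865)/30 and let only the death hazard differ. Death probabilities of 3% and 5% give readmission incidences of 13.30% and 13.17%, a false difference of 0.13 points. Probabilities of 5% and 10% give 13.17% and 12.83%, or 0.34 points.

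**Power of a composite.** Add the same 30-day death proportion to both arms (13.5% + x against 10% + x), with 1778 per arm and alpha 0.048. Power is 87.6% at x = 1%, 79.3% at 5% and 71.0% at 10%, against 89.7% for readmission alone.

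**The case against.** A reader might infer that the plan censors deaths. No passage says so; that is only the usual default. A death missing from the VUMC record would leave the patient at risk to the end of follow-up, and with no other censoring one minus Kaplan-Meier for such patients equals the simple proportion. Appendix IV also lists deceased status among the reasons for call ineligibility, and Appendix V counts post-randomization exclusions. That leaves exclusion possible, but the entry may only catch in-hospital deaths misclassified at discharge. The supportable statement is that the handling of death is not specified and that overstatement arises to the extent that deaths are recorded and censored.

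A reader might also infer that the primary result is biased. The documents do not support that. The primary test is a chi-square comparison of 30-day proportions, and counting an unreadmitted death as no readmission follows from the endpoint chosen. Mortality is reported separately by arm, and the false difference from quite unequal deaths is small (0.13 to 0.34 points).

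Nor should the single-arm excess be set against the 3.5-point target difference. The excess occurs in both arms and largely cancels.

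Finally, the time-to-event work is declared unpowered and exploratory, and a Cox model that censors deaths still gives a valid cause-specific hazard ratio. All of this stands. What remains is that the named plot can misstate the probability it will be read as showing, and that a better display is readily available.

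**Conclusion.** The point holds as a low-priority improvement to an exploratory display. The plan names Kaplan-Meier for readmission, gives no rule for death, and enrols patients in whom deaths are foreseeable. If recorded deaths are censored, the control curve at day 30 reads about 0.05 to 0.5 points too high for an assumed 1% to 10% dying unreadmitted by day 45. It then disagrees with the 2x2 rate. With equal deaths in the arms the difference moves by no more than about 0.15 points.

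These sizes rest on constant hazards and on death rates that the documents do not supply. The primary test and the sample size are untouched.

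**What to change.** 1. State how a death before readmission is treated in the 2x2 table, the curve and the Cox model.
2. Replace the Kaplan-Meier plot by Aalen-Johansen cumulative incidence curves by arm, with death as a competing event.
3. Label the Cox estimate a cause-specific hazard ratio for readmission.
4. Add 30-day readmission or death by arm as a sensitivity analysis only. Leave the primary outcome and sample size as they are.

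The coding cost is small, but there are data limits. Survival is listed at 30 days, whereas the plot runs to day 45. Either extract death dates to day 45 or stop the competing-risk curve at day 30. Deaths not recorded in the VUMC record will be missed, and this should be stated beside the figure. The Study Timeline leaves death data out of the January 2018 presentation and allows only VUMC deaths at the interim, so the complete version belongs to the June 2018 analysis. The composite has less power than the primary outcome (71.0% to 87.6% in the cases above) and should be reported with that caution.
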